**Table 4: Laboratory parameters**

Hematology	
White blood cell (WBC) count	Neutrophils absolute count
Red blood cell (RBC) count	Lymphocytes absolute count
Hemoglobin (Hb)	Monocytes absolute count
Hematocrit (HCT)	Eosinophils absolute count
Mean corpuscular volume (MCV)	Basophils absolute count
Mean corpuscular hemoglobin (MCH)	Platelets
Mean corpuscular hemoglobin concentration (MCHC)	
Serum Clinical Chemistry	
Sodium	Alkaline phosphatase (ALP)
Potassium	Alanine aminotransferase (ALT)
Urea	Aspartate aminotransferase (AST)
Creatinine	Gamma glutamyl transpeptidase (GGT)
Albumin	Total Bilirubin
Calcium	Unconjugated bilirubin
Phosphate	Conjugated bilirubin
Glucose	Creatine Kinase
Urinalysis	
Glucose	
Protein	
Blood	
Microscopy (if positive for protein or blood): RBC, WBC, Casts (Cellular, Granular, Hyaline)	
Coagulation	
International normalized ratio	Prothrombin Time
Activated partial thrombin time	

#### 4.2.2.3 Vital Signs

The results of heart rate, respiration rate, pulse rate, pulse oximetry, BP, and body temperature measurements will be listed by participant and time point including the date/time of the assessment, changes from baseline and repeat/unscheduled measurements.

Descriptive statistics (count, mean, SD and median) will be presented by time point for both observed values and changes from baseline.

#### 4.2.2.4 Physical Examination

A Complete Physical Examination will include, but not be limited to, assessment of height, weight, general appearance, head, ears, eyes, nose, throat, neck, skin, as well as cardiovascular, respiratory, abdominal, and nervous systems.

Abnormal baseline/results of the Physical Examination will be documented in medical history.

Any new or aggravated clinically relevant abnormal medical physical examination finding compared to the baseline assessment will be reported as an AE.

#### **4.2.2.5 ECG**

12-lead ECG results will be listed for each participant with overall evaluation by the investigator as Normal, Abnormal or Borderline including clinical significance (CS or NCS).

These evaluations will be summarized via a shift table showing the frequencies and percentages of the baseline evaluation versus the worst post-baseline overall evaluation.

#### **4.2.2.6 Subgroup Analyses**

No analyses for a specific subgroup are planned.

### **4.2.3 Secondary Endpoint – All Cohorts**

#### **4.2.3.1 SARS-CoV-2 neutralizing antibodies**

To evaluate the PD of AZD7442 after a single IM or IV dose, titers of SARS-CoV-2 neutralizing antibodies will be listed for the SAF and summarized for the SES at each time point.

Descriptive statistics for gmean titers (GMT) and geometric mean fold rises will include number of participants, gmean, gSD, 95% CI for the gmean, minimum, and maximum.

The GMTs for nAbs will be calculated for all participants in the SES as the antilogarithm of  $\Sigma(\log_2 \text{transformed titer}/n)$ , ieas the antilogarithm transformation of the mean of the log-transformed titer with base 2, where n is the number of participants with titer information. The gSD for GMT will be calculated as the antilogarithm transformation of the standard deviation of the log-transformed titer. The 95% CI will be calculated as the antilogarithm transformation of the upper and lower limits for a two-sided CI for the mean of the log-transformed titers.

Summary tables will be generated by cohort and route of IMP administration, and separately by cohort, route of administration and COVID-19 vaccination status at baseline (as captured in the eCRF).

#### **4.2.3.2 ADA and nAb to AZD7442 in serum**

To evaluate the immunogenicity profile of AZD7442, the incidence of ADA and nAb to AZD7442 in serum will be assessed and summarized for the ADS (ie, ADS1 for AZD1061, ADS2 for AZD8895 and ADS3 for AZD7442).

The ADA for AZD7442 will be assessed for the individual agents AZD8895 and AZD1061 separately. The respective agent's ADA Evaluatable Analysis Set (see [Table 1: Analysis sets](#)) is to be used for the individual summary. The ADA titer of AZD7442 will be defined as the maximum of AZD8895 and AZD1061 titers at each time point.

Serum samples for AZD8895 and AZD1061 ADA assessments will be conducted utilizing a tiered approach (screen, confirm, titer), and ADA data will be collected at scheduled visits. The ADA results from each sample will be reported as either positive or negative. If the sample is positive in the confirmatory assay, the ADA titer will be reported as well. In addition, the presence of nAb will be tested for all ADA positive samples in the confirmatory assay. The nAb results will consist of a titer result and a subject status reported as positive or negative. Both of these results will be taken as received from the bioanalytical laboratory. A participant is defined as being ADA-positive if ADA evaluable and a positive ADA result in the confirmatory assay is available at any time, including baseline and all post-baseline measurements; otherwise the participant is defined as ADA negative if ADA evaluable.

Specifically for presentation of AZD7442, ADA-positive to AZD7442 is having a positive ADA result to AZD8895 and/or AZD1061 at any time, including baseline and all post-baseline measurements. ADA-negative is having negative ADA results to all evaluable AZD8895 and AZD1061 results at all time, including baseline and all post-baseline measurements. Summaries will include only ADA evaluable subjects for the respective agent.

In the evaluation of ADA results to AZD7442, if a component mAb (ieAZD8895 or AZD1061) is not ADA evaluable, all results from the component would be treated as missing.

ADA sample pos/neg status:

- For a sample of a particular visit, AZD7442 is + for that visit if either AZD1061 and/or AZD8895 is +

ADA subject pos/neg status:

- For a subject, AZD7442 is + if either AZD1061 and/or AZD8895 is + at any visit and if the subject is ADA evaluable for the mAb having the + result

Treatment-induced ADA+:

- For AZD1061, ADA negative at baseline and ADA positive at  $\geq 1$  post-baseline assessments with ADA titer  $\geq 80$
- For AZD8895, ADA negative at baseline and ADA positive at  $\geq 1$  post-baseline assessments with ADA titer  $\geq 160$

- AZD7442 is treatment-induced ADA+ if either AZD8895 and/or AZD1061 is treatment-induced ADA+

Treatment-boosted ADA+:

- For AZD1061 or AZD8895, Baseline positive ADA titer that was boosted to  $\geq 4$  - fold during study period
- AZD7442 is treatment-boosted ADA+ if either AZD8895 and/or AZD1061 is treatment-boosted ADA+

Treatment-emergent ADA+:

- For AZD1061 or AZD8895, either treatment-induced ADA+ or treatment-boosted ADA+
- AZD7442 is treatment- emergent ADA+ if either AZD8895 and/or AZD1061 is treatment- emergent ADA+

Persistently ADA+:

- For AZD1061, participants who are Treatment-emergent ADA positive, and having ADA post-baseline positive with ADA titer  $\geq 80$  at  $\geq 2$  post-baseline assessments (with  $\geq 16$  weeks between first and last positive) or positive with ADA titer  $\geq 80$  at last post-baseline assessment
- For AZD8895, participants who are Treatment-emergent ADA positive, and having ADA post-baseline positive with ADA titer  $\geq 160$  at  $\geq 2$  post-baseline assessments (with  $\geq 16$  weeks between first and last positive) or positive with ADA titer  $\geq 160$  at last post-baseline assessment
- AZD7442 is persistently ADA+ if either AZD8895 and/or AZD1061 is persistently ADA+

Transiently ADA+

- For AZD1061, participants who are Treatment-emergent ADA positive, and having at least one post-baseline ADA positive assessment with titer  $\geq 80$  and not fulfilling the conditions of persistently positive
- For AZD8895, participants who are Treatment-emergent ADA positive, and having at least one post-baseline ADA positive assessment with titer  $\geq 160$  and not fulfilling the conditions of persistently positive
- For AZD7442, treatment-emergent ADA positive and not fulfilling the conditions of persistently positive.

The number and percentage of AZD7442, AZD8895 and AZD1061 ADA-evaluable positive/negative participants in each cohort will be determined. The number of ADA-

evaluable participants in the cohort will be used as the denominator for percentage calculation.

To evaluate the ADA responses to AZD7442, AZD8895 and AZD1061 in serum the following analyses will be presented:

- The date and time of the blood samples collected for assessment of ADAs (samples to confirm the presence or absence of anti-AZD7442 (AZD8895 and AZD1061) antibodies from pre-dose Day 1 to Day 366, including the titer for samples confirmed positive for ADA) and neutralizing Antibodies (nAbs) will be listed. Tabulations will be provided for each cohort. The listings will be based on the SAF, the tabulations on the ADS1/2/3 respectively.
- The results of the ADA assessments will be listed for each participant and time point. This will include the classification of the response (positive/negative) and the measured titers where appropriate. Summary tables will be presented, by weight categories, dose, and route of administration as well as overall by route of administration, for the number and percentage of participants with positive/negative results at each time point, based on the ADS1/2/3 respectively.

In addition, the ADA titers (n, median, minimum, and maximum) will be summarized by cohort, route of administration (IM or IV) and weight categories (1 to 4 and all) for all participants with a positive confirmatory assay result at each time point; this tabulation will include a summary of the highest titer across all time points for each participant.

The impact of ADA on PK, PD, and association with AEs and SAEs will be assessed using the graphical and/or tabular displays.

For each cohort and by route of administration, spaghetti plots of individual PK concentration versus time profile by ADA subject status (positive or negative differentiated in the figure via color and/or line style) will be produced on semi-logarithmic scale. AZD7442, AZD8895 and AZD1061 concentrations will be presented separately.

For each cohort and by route of administration, spaghetti plots of nAb titer versus time profile by ADA subject status (positive or negative differentiated in the figure via color and/or line style) will be produced on semi-logarithmic scale.

#### **4.2.4 Secondary Endpoint – Cohort 1 (Prophylaxis)**

To evaluate the incidence of SARS-CoV-2 infections with or without COVID-19 symptoms after a single IM or IV dose of AZD7442 in pediatric participants, when a participant develops at least one of the COVID-19 qualifying symptoms (see Section [Disease Characteristics4.1.6](#)), an unscheduled visit is performed and a SARS-CoV-2 RT-PCR test is performed to confirm the participant is positive. Additionally, to identify

symptom-free SARS-CoV-2 infections, serology testing is performed at each visit. Any positive SARS-CoV-2 test result indicating infection as well as any symptoms will be reported as an AE.

Incidence will be determined by AE and summarized via frequency and proportion of participants in the SAF by weight categories and route of administration. SARS-CoV-2 serology test results will be summarized by count and number of observations for each timepoint and cohort.

This summary will be repeated for participants in the mFAS.

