1.3 Schedule of Activities

Table 1 summarizes the SoA at screening for all participants. **Table 2** and **Table 3** summarize the SoA during the main study for neonates (modified sample collection) and non-neonates, respectively.

Table 1 Schedule of Activities: Screening Period (All Participants)

Procedure/study day	Day -7 to Day 1 ^a	For details, see section:
Informed consent/assent	X	5.1
Assignment SID number ^b	X	6.3
Demographics and risk categorization	X	5.1
Medical history	X	NA
Complete physical examination, including height and weight	X	8.2.1
Vital signs (including pulse oximetry)	X	8.2.2
Triple 12-lead ECG	X	8.2.3
Serum chemistry, hematology, urinalysis ^c	X	8.2.4

Table 1 Schedule of Activities: Screening Period (All Participants)

Procedure/study day	Day -7 to Day 1 ^a		For details, see section:
Coagulation	X		8.2.4
Urine pregnancy test (post-pubertal females only) ^d	X		8.2.4.5
Assessment of SAEs	X		8.3
Concomitant medications	X		6.5
Serum sample for SARS-CoV-2 serology (anti-nucleocapsid) testing (all participants other than neonates)	X		8.5.3.2
Verify eligibility criteria	X		5.1, 5.2
Screening criteria specific to each cohort	Cohort 1 Pre-exposure prophylaxis	Cohorts 2 and 3 Treatment of COVID-19	For details, see section:
Documented SARS-CoV-2 RT-PCR test taken \leq 3 days before Day 1 ^c OR Rapid SARS-CoV-2 antigen test (for assignment to study cohorts) per local standard of care authorized for screening or diagnosis	X (negative)	X (positive)	8.6.1
COVID-19 Symptom screen	NA	X (Yes)	5.1

^a Screening activities may be collected over more than one visit during the 7-day screening window if necessary; if screening and dosing occur at the same visit, only one evaluation is required, unless otherwise specified. The sample taken closest to dosing and prior to dosing is considered the baseline sample.

^b Assigned by the IRT system. See Section [6.3](#) for further information.

^c Collection of urine samples for urinalysis from participants who are unable to provide urine samples is not mandatory provided that a reasonable attempt has been made to collect the samples.

^d If urine tests positive or is indeterminate, a quantitative serum β -hCG will be performed for confirmation before the participant is enrolled in the study. Pregnancy testing is for baseline purposes only, and a participant with a positive urine pregnancy test can still participate in the study.

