8.5.1 Total Blood Volume

Blood volume estimates are provided in **Table 16**. For participants other than neonates, the total estimated blood volume to be collected during the study is approximately 73 mL per participant. For neonates, only safety and PK samples will be collected and the total estimated blood volume to be collected during the study is approximately 22 mL per participant. The total volume can be adjusted by age and the body weight of the participant per local ethics requirements. Where necessary, the visit windows in the SoA can be used to collect samples across a number of days. When sample collection occurs over ≥ 2 days for a given study visit, participants are required to visit the site at least once per study visit. If practical, additional sample collection can take place at home visits as long as the samples are obtained per protocol by qualified personnel. If it is not possible to obtain sufficient blood from a participant at a given study visit, the order of the samples will be prioritized according to the key requirements of the study and the following hierarchy will be applied: safety (ie, serum chemistry, hematology, coagulation), PK, SARS-CoV-2 neutralizing antibodies, and ADA (see Laboratory Manual). For participants receiving IV infusions of AZD7442, blood samples are to be collected from the opposite side of the body to the IV infusion at Visit 1.

Table 16 Blood Volume Estimates

Visit (study day \pm visit window)	Estimated blood volume for neonates ^a	Estimate blood volume for all other participants ^b
Screening Visit (Day -7 to Day 0)	3.7 mL	6.3 mL
Visit 1 (Day 1 \pm 0)	1.2 mL (IV only)	6.0 to 8.5 mL ^{c, d}
Visit 2 (Day 4 to 15 \pm 2)	1.2 mL	2.5 mL
Visit 3 (Day 31 + 5)	4.9 mL ^e	14.8 mL
Visit 4 (Day 92 \pm 5)	2.6 mL ^e	10.3 to 12.8 mL ^d
Visit 5 (Day 183 \pm 10)	3.5 mL ^e	13.0 mL
Visit 6 (Day 366 \pm 15)	4.9 mL ^e	14.8 mL
Total from screening to Day 366	20.8 to 22.0 mL	67.7 to 72.7 mL

^a For neonates, only safety and PK samples will be collected.

^b For participants other than neonates, the following hierarchy will apply if it is not possible to obtain blood for all samples: (1) safety, (2) pharmacokinetics, (3) SARS-CoV-2 neutralizing antibodies, and (4) anti-drug antibodies.

^c At Visit 1, participants receiving AZD7442 IV will have an extra 2.5mL blood sample taken for post-dose PK sampling.

^d At Visit 4, participants in Cohort 1 will also have an additional 2.5mL taken for SARS-CoV-2 serology.

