8.5.3.2 SARS-CoV-2 Serology

Serum samples will be collected to assess SARS-CoV-2 antigen-specific antibody levels at baseline from all participants. Serostatus will also be collected from non-neonates in Cohort 1 according to the SoA (Table 3). Baseline serostatus and time to seroconversion in participants receiving AZD7442 will be determined using a validated SARS-CoV-2 nucleocapsid antigen assay operated by an authorized laboratory. Serologic assessment to S (spike), RBD, and nucleocapsid antigens may also be assessed quantitatively using a validated multiplexed meso scale discovery immunoassay.

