**Table 1: Analysis sets**

Population/Analysis Set	Description
Screened Population Set (SPS)	All participants who signed the ICF. Unless otherwise stated, this set will be used for the presentation of disposition data.
Full Analysis Set (FAS)	All participants who received the IMP, irrespective of their protocol adherence and continued participation in the study. Participants who withdraw consent or assent to participate in the study will be included up to the date of their study termination.
Modified Full Analysis Set (mFAS)	All participants who are in the FAS, excluding participants who were assigned to Cohort 1 by rapid COVID-19 test, but have a positive confirmatory test.
Safety Analysis Set (SAF)	All participants who have received IMP.
PK Analysis Set (PKS)	All participants who received AZD7442 and from whom PK blood samples are assumed not to be affected by factors such as protocol violations, and who had at least one quantifiable serum PK observation post-dose, will be included in the PK analysis dataset.
AZD1061 ADA Evaluable Analysis Set (ADS1)	A participant is AZD1061 ADA evaluable if in the SAF and having a non-missing baseline AZD1061 ADA result and at least one non-missing post-baseline AZD1061 ADA result.
AZD8895 ADA Evaluable Analysis Set (ADS2)	A participant is AZD8895 ADA evaluable if in the SAF and having a non-missing baseline AZD8895 ADA result and at least one non-missing post-baseline AZD8895 ADA result.
AZD7442 ADA Evaluable Analysis Set (ADS3)	All participants who are AZD8895 ADA evaluable and/or AZD1061 ADA evaluable.
SARS-CoV-2 nAb Evaluable Analysis Set (SES)	All participants in the Safety Analysis Set from whom blood samples were assumed not to be affected by factors such as protocol violations, and who had at least one quantifiable serum titer observation post dose.

Generally, all listings will be prepared based on the SAF unless otherwise stated.  
Disposition data will be listed for the SPS.

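### SAP 4.2.4 counts Cohort 1 neonates as free of symptom-free infection although the protocol schedules no post-dose serology for them

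*SAP*

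**What the plan says.** The Cohort 1 secondary endpoint is SARS-CoV-2 infection with and without symptoms. SAP 4.2.4 gives two ways of finding it. A qualifying symptom leads to an unscheduled visit with RT-PCR. To find the remaining "symptom-free SARS-CoV-2 infections, serology testing is performed at each visit". Positive results are reported as AEs, and then: "Incidence will be determined by AE and summarized via frequency and proportion of participants in the SAF by weight categories and route of administration". SAP Table 1 defines the SAF as "All participants who have received IMP". Because the section concerns Cohort 1, I read the denominator as the Cohort 1 members of the SAF. The summary is repeated in the mFAS, which is the FAS "excluding participants who were assigned to Cohort 1 by rapid COVID-19 test, but have a positive confirmatory test".

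The protocol describes a narrower serology scheme:

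- Table 1 (screening) lists "Serum sample for SARS-CoV-2 serology (anti-nucleocapsid) testing (all participants other than neonates").
- Section 8.5.3.2: "Serostatus will also be collected from non-neonates in Cohort 1 according to the SoA".
- Table 3 (non-neonates) has a Cohort 1 serology row at Visits 3 to 6 and at early discontinuation. Table 2 (neonates) has no such row through Day 366.
- Section 8.5.1: "For neonates, only safety and PK samples will be collected".
- The footnotes to Tables 2 and 3 limit the Day 8 RT-PCR to Cohorts 2 and 3. After Day 1, Cohort 1 is swabbed only when qualifying symptoms occur.

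**The concern.** A proportion needs a denominator of people in whom the event could have been seen. Serology is the only scheduled way to see an infection without symptoms in Cohort 1, and neonates do not have it after dosing. The SAP nevertheless describes serology as universal and divides by everyone dosed, so an untested neonate enters the table as a participant without symptom-free infection.

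The table is split by weight category and route. Neonates can be expected mainly in the lowest band (1.5 to under 5 kg), so a low figure there may reflect absence of testing. Neither of the SAP's other summaries repairs this. The mFAS removes participants only for a positive confirmatory test. The separate serology summary shows the number of observations by timepoint and cohort, not by weight category.

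**Working it through.** **Is there a figure to reproduce?** No. The documents give no expected rate or precision for this endpoint. The counts used below come from protocol Table 5, whose Cohort 1 columns add up as printed: IM 6 + 1 + 6 + 6 = 19 and IV 4 + 6 + 1 + 1 = 12, so the Cohort 1 minimum is 19 + 12 = 31.

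**Other inputs from Table 5 (planned minima).** Cohort 1 under 1 year: 6 IM + 1 IV = 7. Of these, at least 2 are neonates and at least 2 are aged 1 month to under 1 year, so at most 7 - 2 = 5 of a group of 7 are neonates.

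**Assumptions.** (a) At least one Cohort 1 neonate was dosed. (b) The true risk p of symptom-free infection is the same in neonates and other infants. (c) No incidental positives occur in neonates. (d) Tested infants have complete detection. (e) For the weight-band rows, all 7 infants are in the lowest band. The documents do not cross age with weight, so (e) is only illustrative.

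**Formula.** In a stratum of N participants with m neonates, let f = m/N. Expected detected symptom-free infections are p(N - m), so the expected proportion on the SAF denominator is p(N - m)/N = p(1 - f). On a tested-only denominator it is p(N - m)/(N - m) = p, and it is not estimable when m = N.

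| Stratum | m/N | f | Reported/true | Reported if p = 20% (assumed) |
|---|---|---|---|---|
| No neonates | 0 | 0 | 1.000 | 20.0% |
| Infants, minimum neonates | 2/7 | 0.286 | 0.714 | 14.3% |
| Infants, maximum neonates | 5/7 | 0.714 | 0.286 | 5.7% |
| Neonates only | 2/2 | 1 | 0 | 0% |
| Whole Cohort 1 minimum | 2/31 | 0.065 | 0.935 | 18.7% |

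The understatement is therefore 29% for 2 of 7 and 6.5% over the planned cohort. A neonate-only cell reports about 0% at any true rate. Such a cell is conceivable if weight and route are crossed: Table 5 plans as few as 1 Cohort 1 infant under 1 year by IV and lets neonates receive either route.

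**Absolute size.** With 2 neonates and p = 20%, the expected number of missed infections is 2 × 0.20 = 0.4.

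**What is not affected.** Symptom-triggered RT-PCR applies to neonates too (Table 2 footnote), so the symptomatic component keeps its valid denominator. Total incidence is therefore understated by a smaller fraction than the symptom-free part whenever there are symptomatic cases.

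**The case against.** The strongest reply is that the effect may be nil. SAP Section 2 records that enrolment stopped and that the full analysis set holds 46 participants instead of 100. The minima in Table 5 belong to the larger plan, and the documents give neither the number of neonates nor the Cohort 1 total. The endpoint is also secondary, descriptive and uncontrolled. No comparison between weight bands is planned, and the likely number of missed infections is below one. SAP 3.3.1 requires each table to show its denominator, and the protocol is open about the neonatal exception.

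Much of this stands and limits the size and urgency. It does not remove the error: showing the SAF count as denominator does not tell a reader that some of those counted were never tested.

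Several stronger readings are tempting but not supported:

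- *The lowest weight band is biased towards zero as a matter of fact.* This depends on neonates having been dosed, and the band can also hold older infants who do have serology.
- *A symptom-free infection in a neonate can never be counted.* Protocol 8.1.1 records positive SARS-CoV-2 tests as AEs and the SAP determines incidence by AE, so an incidental positive would enter.
- *Neonates have no serology at any time.* Protocol 8.5.3.2 also says baseline samples come from every participant, which conflicts with Table 1 and Section 8.5.1. Only the absence of post-dose serology is uncontested, and that is what matters for incidence.
- *Small infants will also lose serology because it is missing from the blood-priority list.* The list does omit it, but Table 16 budgets 2.5 mL for Cohort 1 serology at Visit 4, and nothing shows that samples will be dropped.

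**Conclusion.** The point holds in conditional form. The SAP sentence contradicts the protocol, and the SAF denominator counts any dosed Cohort 1 neonate as free of an infection for which no scheduled test exists. If such neonates are in the analysis set and the true risk is equal, the symptom-free proportion is understated by the fraction f: 29% for 2 neonates among 7 infants and 6.5% across the planned Cohort 1 minimum, with a neonate-only cell close to 0% regardless of the truth. If no Cohort 1 neonate was dosed, only the wording error remains. A reader might infer from a low figure in the smallest children that they were better protected; the planned table could not support that. The matter should be corrected before the final tables, but it does not touch the primary PK or safety endpoints.

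**What to change.** In SAP 4.2.4:

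1. State that serology is scheduled in Cohort 1 non-neonates at Visits 3 to 6 and at early discontinuation.
2. Keep all dosed Cohort 1 participants as the denominator for symptomatic, RT-PCR-confirmed infection.
3. For symptom-free infection, use Cohort 1 participants who are anti-nucleocapsid negative at baseline and have at least one post-baseline result. The baseline condition stops infections that preceded dosing from counting as new.
4. Show the number tested in each weight and route cell and mark neonates as not assessed. List any incidental positive in a participant outside this denominator separately.
5. Apply the same rule to the mFAS repeat.

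This follows what the SAP already does for ADA, where percentages are based on participants with a baseline and a post-baseline result.

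The cost is SAP wording and one or two table columns, with no extra blood, visits or data. The downside is a smaller denominator and wider uncertainty for the symptom-free component. One limit remains: a child tested only at Day 31 counts the same as one tested through Day 366, so the existing summary of observations by timepoint should be read alongside.
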